### **Secondary Outcome Measures**

- Number of patients in each BARSCORE category after laparoscopic bariatric surgery
- Distribution of supplementation requirements by surgical technique
- Inter-center variability in score application

## **Sample Size Determination**

This is an exploratory study in which the sample size cannot be numerically justified in usual terms. Reliable data on the expected magnitude of differences are currently unknown, given that homogeneous results regarding the risk of malnutrition and vitamin deficiencies are not available in the literature.

At least 1,200 patients will be included, corresponding to patients from the study period (January 2015 to October 2022) at the main investigational center (Bellvitge Hospital). This number seems reasonable in an exploratory context, supported by additional references with similar sample sizes in this field.

## **Statistical Analysis Plan**

### **Descriptive Statistics:**

- Categorical variables: number of cases and percentages
- Continuous variables: mean and standard deviation

### **Primary Analysis:**

1. **Coherence:** Spearman correlation test (significance:  $p < 0.05$ )
2. **Concordance:** Two-way ANOVA assuming normality and homoscedasticity (significance:  $p < 0.05$ )
3. **Ease of application:** Descriptive analysis with percentages (target: >70% favorable responses)

**Risk Factors:** Initial risk factors include sociodemographic data (age, sex, BMI), comorbidities, type of bariatric surgery, and surgical complications.

## **TIMELINE AND WORK PLAN**

- **Study initiation:** October 2024
- **Data collection:** October 2024 - December 2024
- **Database cleaning and statistical analysis:** January 2025 - March 2025
- **Survey administration:** March 2025 - April 2025
- **Final report completion:** October 2025

## ETHICAL CONSIDERATIONS

### Data Management

An electronic data collection questionnaire will be designed in REDCap. The data collection system will be online via web, with data stored on an IDIBELL server with high security measures. Each investigator will have password-protected access limited to their center's data.

### Patient Privacy

Given that this study is based on anonymized medical record information and considering the difficulty of contacting patients and the number of patients lost to follow-up, written consent will not be requested.

Patients will be identified by an identification number assigned when entering the database, removing medical record numbers and dates of birth. Only an IDIBELL statistician and one reference person per center will have access to patient identification correlations, governed by GDPR Article 14 and Spanish Organic Law 3/2018.

### Ethics Committee Approval

Clinical research ethics committee authorization is attached to the protocol.

## RESOURCES AND INFRASTRUCTURE

Resources and infrastructure from each participating hospital will be used for patient recruitment according to usual surgical activity. Computer infrastructure will be provided by IDIBELL through the online database for data collection and analysis.

## EXPECTED BENEFITS

This study will create and validate a score that allows measuring and quantifying supplementation needs after bariatric surgery in a standardized and comparable manner, enabling comparison between techniques, surgeons, and centers.

The BARSCORE will provide objective information to assess pros and cons of each surgical technique individually for each patient:

- **Pros:** Total weight loss percentage (%TWL) and comorbidity resolution
- **Cons:** Short-term surgical complications (Clavien-Dindo) and long-term complications (BARSCORE)

This will contribute to providing more comprehensive information for shared informed consent.

**Correct Answer: GRADE I**

## APPENDIX B: EASE OF APPLICATION SURVEY

### Instructions for Investigators

Please answer the following questions about the BARSCORE classification system based on your experience reviewing the cases and the score definition.

#### **1. How long did it take you to understand the score?**

- 5–10 minutes
- 10–20 minutes
- >20 minutes
- I did not understand it

#### **2. Do you think the score is simple?**

- Yes
- No

#### **3. Do you think the score is reproducible?**

- Yes
- No

#### **4. Do you think the score is logical?**

- Yes
- No

#### **5. Do you consider that the score could be useful for your patients?**

- Yes
- No

#### **6. Do you think the score will be beneficial from a hospital perspective?**

- Yes
- No

#### **7. Please note positive aspects of the score (optional):**

---

#### **8. Please note negative aspects of the score (optional):**

---

## APPENDIX C: BARSCORE CLASSIFICATION SYSTEM

BARSCORE	
Bariatric Surgery Supplementation Classification	
0	No Supplements No supplementation
I	Routine/Protocol Supplements Standard supplementation with multivitamins, calcium, folic acid, vitamin B12, vitamin D according to local protocol*
II	Oral Supplements (+Non-Protocol B12) IIA: Oral iron, folic acid, vitamin D, or vitamin B12 at higher than routine doses. Maximum 2 supplements.* IIB: Vitamin A, B1, K, E, Zinc, or Copper oral. OR >2 supplements, even if category IIA.
III	Parenteral Supplements (except B12) IIIA: Intravenous iron, parenteral vitamin K. IIIB: Parenteral vitamin B1 or A. Other parenteral supplementation.
IV	Mild Malnutrition Requires protein modules ± oral enteral nutrition regularly
V	Severe Protein-Energy Malnutrition Requires enteral nutrition via NG/NJ tube or parenteral nutrition, OR surgical reversal indication due to malnutrition/uncontrollable diarrhea

**\*Protocol definition:** 2 tablets/day adult multivitamins plus minerals (iron, folic acid, thiamine) or 1 tablet/day bariatric-specific multivitamin plus: elemental calcium ( $\leq$ 2400 mg/d), vitamin D ( $\leq$ 3000 IU/d), iron ( $\leq$ 60 mg/d), vitamin B12 ( $\leq$ 500 mcg/d oral or  $\leq$ 1000 mcg/month IM-SC).

### Score Application Considerations

- Patient categorization requires >2 years follow-up with analytical control and evaluation by endocrinologist + dietitian-nutritionist
- Patients are included in a category if they required supplementation at any time from the 3rd month post-surgery until present, even if currently not needed
- Supplements administered routinely by hospital protocol without demonstrated analytical deficit are excluded from categories >I

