## **HYPOTHESIS**

The BARSCORE score will allow estimation of supplementation needs for vitamins, micronutrients, and proteins after bariatric surgery.

The BARSCORE score will be a coherent score, so that more complex surgeries will have higher scores in the score with a Spearman correlation test with  $p < 0.05$ .

The BARSCORE score will be a score with a high level of concordance since different investigators from each center will score the presented cases in the same way, obtaining a two-way analysis of variance with  $p < 0.05$ .

The BARSCORE score will be an easy-to-apply score since it will obtain a percentage of favorable results greater than 70% in the score evaluation survey.

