### **Primary Outcome Measures**

1. **Score Coherence** (Time Frame: Minimum 2 years post-surgery follow-up)
  - Spearman correlation coefficient between surgical complexity and BARSCORE score
  - Success criterion:  $p < 0.05$
2. **Score Concordance (Reproducibility)** (Time Frame: Single assessment after database completion)
  - Two-way ANOVA analysis of responses from different investigators on standardized cases
  - Success criterion:  $p < 0.05$
3. **Ease of Application** (Time Frame: Single assessment after database completion)
  - Percentage of favorable responses in evaluation survey
  - Success criterion: >70% favorable responses

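### The 0-versus-I step of BARSCORE can follow prescribing policy rather than need, and if policy differs by technique or centre it can meet the coherence criterion by itself

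*Combined protocol and SAP*

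**What the plan says.** Appendix C defines Grade 0 as no supplements and Grade I as "Standard supplementation with multivitamins, calcium, folic acid, vitamin B12, vitamin D according to local protocol". Neither definition mentions a laboratory deficit. The Score Application Considerations add one rule about deficits: "Supplements administered routinely by hospital protocol without demonstrated analytical deficit are excluded from categories >I". They also classify a patient by anything required from the third month after surgery onward, even if it has since stopped.

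The answer key in Appendix A applies Grade I in this way. Case 2 (duodenal switch), Case 3 (gastric bypass) and Case 14 (sleeve) are on routine or multivitamin supplements, no deficit is described, and all three are keyed Grade I.

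The Hypothesis section expects that "more complex surgeries will have higher scores in the score with a Spearman correlation test" will show this at p below 0.05. Primary Outcome Measures names the statistic as the "Spearman correlation coefficient between surgical complexity and BARSCORE score", and the Primary Analysis lists the "Spearman correlation test" with the same threshold. No minimum rho is set, there is no adjustment for centre or local protocol, and no analysis merges grades 0 and I. On size, "At least 1,200 patients will be included", and the section states that "the sample size cannot be numerically justified in usual terms".

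**The concern.** The score is meant to estimate supplementation need. Above Grade I, routine supplements without a deficit do not count, so the grade has some tie to need. Between 0 and I there is no such condition, and the grade records whether routine supplements were given.

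Suppose routine supplements are given more often after bypass or switch than after sleeve. The 0/I split then rises with technique because of policy, and the Spearman test counts that rise as coherence. A similar effect arises if each centre treats all its patients alike, but centres differ both in policy and in their mix of techniques. In either case the first primary outcome could be declared met although need beyond protocol is the same for every technique. Nothing in the planned analysis would separate the two explanations.

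**Working it through.** The plan has no power or effect-size figure to reproduce. The check asks how large a correlation is needed, and how much of it the 0/I step can supply.

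**Inputs from the documents:** N = 1,200 (Sample Size Determination); p < 0.05, taken as two-sided (Primary Analysis); three technique groups (Procedure); eight ordered levels 0, I, IIA, IIB, IIIA, IIIB, IV, V (Appendix C).

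**Assumptions, because the documents give no figures:** groups of 500/500/200 (sleeve/bypass/switch); 25% or 50% of every group above Grade I, spread evenly over the six higher levels and unrelated to technique; never-supplemented shares among the rest of 40/10/0%, 20/5/0% or 10/2/0%.

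**Step 1, the threshold.** Critical rho = t/√(N − 2 + t²). With t = 1.962, this is 1.962/√(1198 + 3.849) = 0.057, about 0.3% of rank variance (0.057² = 0.003).

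**Step 2, expected rho from the 0/I step alone (25% above Grade I, shares 40/10/0%).**
- The midranks of Grade 0 and Grade I differ by half the number of patients not above Grade I: 900/2 = 450.
- Grade 0 shares of the whole group are 0.75 × 0.40 = 0.30, 0.75 × 0.10 = 0.075 and 0. These lower the mean grade rank by 135, 33.75 and 0.
- Technique midranks deviate from their mean by −350, 150 and 500. Their SD is √[(500·350² + 500·150² + 200·500²)/1200] = 319.5.
- Covariance = (500·350·135 − 500·150·33.75)/1200 = 17,578.
- Grade 0 holds 0.15625 of all patients and Grade I 0.59375. SD of grade ranks = √[(1200²/12)(1 − 0.15625³ − 0.59375³ − 6(0.25/6)³)] = 307.2.
- rho = 17,578/(319.5 × 307.2) = 0.18.

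**Step 3, all scenarios.** Rho is from the same formula. Pass rates are simulated, with at least 1,000 replicates per scenario; repeated runs differ by a few percentage points.

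| Never supplemented (sleeve/bypass/switch) | 25% above I: rho | pass | 50% above I: rho | pass |
|---|---|---|---|---|
| 40/10/0% | 0.18 | 100% | 0.07 | about 73% |
| 20/5/0% | 0.10 | about 90% | 0.04 | about 28% |
| 10/2/0% | 0.05 | about 43% | 0.02 | about 10% |

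As a hand check of the 43%: 0.0509 × √1198 = 1.76, and P(Z > 1.96 − 1.76) is about 42%.

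**Step 4, grades 0 and I merged.** Rejections fall to about 4% to 6% in all six scenarios, the nominal rate.

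**Step 5, the centre route.** Take two centres of 600 with every patient at 0 or I and the same policy for all techniques within each centre. Technique mixes of 60/30/10 and 40/40/20 with 80% and 100% supplemented give rho 0.070, p = 0.016. The route needs a real contrast in mix: mixes of 50/40/10 and 45/40/15 with 50% and 100% supplemented give rho 0.038, p = 0.18, and identical mixes give rho 0.

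**Step 6, uniform policy.** If the routine share is the same in every technique and centre, expected rho is 0 and the test rejects at its nominal rate.

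**The case against.** The strongest reply is that the premise is undocumented. Appendix C gives a single protocol definition with no split by technique, and the keyed cases put sleeve, bypass and switch patients alike at Grade I. Grade 0 is also narrow: a patient must have needed nothing since month three, and Case 6, unsupplemented now, is still keyed IIIA. A never-supplemented share of 40% after sleeve has no support in the documents. All of this stands, and it is why the point is conditional. It does not close the matter, because the definition mostly sets upper limits and refers to local protocol, and Case 14 refers to the patient's own centre's protocol.

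Second, the Introduction expects deficiency especially after mixed and hypoabsorptive techniques. If that is so, the correlation should survive merging. That is likely, but it is what the study sets out to show.

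Third, 0 versus I is a defined level of therapeutic effort, so making a collapsed scale the only gate would test a different score. This stands, and the full scale should remain.

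Fourth, the permissive criterion is part of the cause, since any small imbalance can pass. This also stands; a confidence interval for rho would expose weak results. It would not show where the correlation comes from.

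Fifth, Secondary Outcome Measures already covers counts per category, supplementation by technique and inter-centre variability. Only the breakdown by centre and the merged analysis would be new.

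**Conclusion.** The concern holds in conditional form. Grade I needs no deficit, the deficit rule acts only above it, and a rho of about 0.057 meets the coherence criterion. If routine supplementation differs by technique, or by centre together with technique mix, the lowest step can produce a significant result with no difference in need beyond protocol. Under the assumptions above, the chance ranges from about 10% to 100%. It falls as the policy gap narrows and as more patients lie above Grade I, and it is nominal when policy is uniform.

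A reader might infer more, and the documents do not support it:
- They do not report that routine supplementation differs by technique or centre, so a significant result cannot be called an artefact in advance.
- Grade 0 may reflect no need or non-adherence, so the step is not purely policy.
- The plan gives no purpose for the deficit rule, so it cannot be faulted for failing at one.

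**What to change.** In the Statistical Analysis Plan, Primary Analysis item 1:

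- Keep the Spearman analysis on the full 0 to V scale.
- Add a prespecified Spearman analysis with grades 0 and I merged into one level (no need beyond protocol).
- Report rho with a 95% CI for both.
- Tabulate grades 0 and I by technique and by centre.
- State in advance that, if the correlation does not hold on the merged scale, the coherence result will not be interpreted as greater supplementation need beyond protocol after more complex surgery.

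The cost is one recode of data already collected, one extra analysis and one table. The downside is that the merged version ignores real differences between needing nothing and needing only routine supplements, which is why it sits beside the full-scale analysis and does not replace it.
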